PREG2 protocol synopsis

Name	PREG2					
Title	PRE vention of intrauterine adhesion after adhesiolysis with novel tri-block de G radable polymer film. NCT04963179.					
Protocol version date	December 16th 2022					
Rationale for study	PREvention of intrauterine adhesion after adhesiolysis with nove tri-block deGradable polymer film. NCT04963179. December 16th 2022 Intrauterine adhesions (IUA) are defined as "fibrous strings at opposing walls of the uterus and/or cervix leading to partial or complete obliteration of the cavity" ¹ . IUA can lead to recurrent pregnancy loss infertility, abnormal placentation, menstrual abnormalities, and pain. ^{1,7} Treatment by hysteroscopic lysis is recommended if the patient has clinical symptoms. However, one of the greatest challenge is the recurrence of adhesive disease ^{1,3} : the recurrence rate after intrauterine synechiae lysis is 20% to 32% and 42% to 60% in the case of severe synechiae lysis is 20% to 32% and 42% to 60% in the case of severe synechiae lysis is 20% to 32% and recurrences makes reproductive outcomes unsatisfactory, even after hysteroscopic treatment ⁸ . It is acknowledged that the use of an intrauterine barrier potentially reduces postoperative adhesion reformation. However, existing barriers have suboptimal efficacy due to their limited residence time in the uterus (HA gel) or need of manual removal (IUD, balloon, amnior graft). As a result, a golden standard to prevent adhesive disease does not exist. Therefore, there is an unmet medical need for an evidence based effective secondary prevention method. Hence the evaluation of the efficacy of the anti adhesion effects of Womed Leaf after adhesiolysis. Name : Womed Leaf Device group : Anti-adhesion barrier					
Study device						

¹ Hooker et al., Prevalence of intrauterine adhesions after the application of hyaluronic acid gel after dilatation and curettage in women with at least one previous curettage: short-term outcomes of a multicenter, prospective randomized controlled trial. Fertility and Sterility. 2017;107(5):0015-0282.

² Tuuli MG et al. Uterine synechiae and pregnancy complications. Obstet Gynecol 2012 ; 119 :810-4

³ Warembourg S et al. Prevention and treatment of intrauterine synechiae : Review of literature. J Gynecol Obstet Biol Reprod. 2015 Apr ; 44 :366-79.

⁴ Pabuccu 1999

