	16	Responder rate: Percentage of patients with an improvement of
	10.	one clinical category i.e from Severe to Moderate or from Moderate to Mild
Inclusion criteria	1.	Women with moderate or severe intrauterine adhesions according
		to the AFS classification, i.e AFS score >=5, confirmed by
		hysteroscopy right before adhesiolysis
	2.	Scheduled for hysteroscopic adhesiolysis
	3.	Age above or equal to 18
	J.	

Exclusion criteria	 Subjects who can comply with the study follow-up (second look hysteroscopy) and other study requirements. Subjects who agree to refrain from intercourse or use a reliable form of barrier contraception to prevent unintended pregnancy until the follow-up hysteroscopy. Subjects who agree to avoid all intrauterine devices (IUDs) until the follow-up hysteroscopy. Pre-operative criteria Post menopause Pregnant (confirmed by a positive pregnancy test) or lactating Abnormal uterine cavity according to ESHRE classification I to V such as unicornis, bicornis, septate, duplex Known or suspected endometrial hyperplasia History of cervical or endometrial cancer Active pelvic infection or history of pelvic peritonitis History of endometrial ablation Known contraindication or hypersensitivity to Womed Leaf component Current participation in another clinical investigation that has not yet received the primary endpoint. Any other condition that makes participation in the study contrary to the patient's best interests. Intra-operative criteria, post adhesiolysis: Perforation during adhesiolysis Uterine depth < 5cm or > 10cm 					
Intervention technique	Hysteroscopic adhesiolysis using tools according to local practice of the participating center.					
Procedure and drug regimen	According to local practice of the participating site					
Data collection and Follow up schedule	 Assessment of IUA severity at the beginning and at the end of operative hysteroscopy Assessment of procedure or device related adverse event at 2 weeks and 6 weeks Second-look hysteroscopy at 6 weeks (+/-2 weeks) to assess recurring IUA. All patients will be contacted at 1 year and 2 years (+/- 1 month) by email and/or phone call to assess their pregnancy status. See table below. 					
Timelines	The first patient will be included in Q4 2021. Patient inclusion will last 24 months. Evaluation of the primary outcome will be done by Q1 2024. Total study duration (including long term follow-up): 4 years Data gathering and analysis before manuscript submission: 3 months.					

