Blinding	Open label to the surgeon Blinded to the study subjects and the hysteroscopy evaluator.				
Sample Size Calculation	 Two sided test Confidence interval: 95% (5% alpha/type I error) Power: 90% (10% beta/type II error) Hypothesis*: Control group: mean difference of AFS score = 5 Study group: mean difference of AFS score = 6 Standard deviation: 1,8 ⇒ Sample size: 138 Loss to follow up: 10% ⇒ Total population: 154 subjects with a 1:1 randomization 				
Statistical Analysis Plan	The Intention To Treat (ITT) population is defined by all randomized patients. The safety population is defined by all randomized patients. Standard descriptive statistics will be used. Randomization being stratified on IUA severity, statistical analysis will be adjusted on IUA severity. For the primary effectiveness endpoint (classification of adhesions): A covariance analysis (ANCOVA) with the mean change of AFS score between pre-adhesiolysis and SLH as dependent parameter, with IUA severity stratum as covariate will be conducted to compare the 2 groups. The two-sided 95% Cl of the mean change of AFS score between pre-adhesiolysis and SLH will be estimated independently in each randomization group using standard error (SE). If H0 is rejected and $\Delta_{WOMED} > \Delta_c$ then, superiority of Womed Leaf over no IUA prevention method will be concluded. If the normality of the change of AFS score cannot be assumed, the tertiles of the parameter will be used as a dependent parameter and an ordinal logistic regression model will be used. For the primary safety endpoint, all AE will be presented. For key secondary efficacy endpoints: The list of key secondary endpoints has been hierarchically ordered. For each endpoint, the hypotheses will be tested using a fixed-sequence method following the order defined, using 2-sided statistical tests, all at the same significance level alpha ($\alpha = 0.05$), moving to a second endpoint only after a success on the previous endpoint.				
Applicable Norms	ISO 14155:2020, Good Clinical Practice, 21 CFR Parts 11, 50, 54, 56, and 812, Medical Device Regulation (EU) 2017/745 (MDR) and MDCG 2020-10/1 guidance, Good Clinical Practice for Medical Devices Clinical trials (Decree No. 28, 2022) promulgated by NMPA in 2022.				

		D-7 days (±7days)	D0		2 weeks (+/-1 week)	6 weeks (+/-2 weeks)	1 year (+/-1 month)	2 years (+/-1 month)

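### The non-normality fallback cuts the primary AFS change into tertiles; no power is given for that model, and an uncut severity-adjusted analysis usually has more

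*Combined protocol and SAP*

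**What the plan says.** In the Combined protocol and SAP, the Statistical Analysis Plan row makes ANCOVA on the change in AFS score, with severity stratum as covariate, the primary effectiveness analysis. It then adds a fallback: "If the normality of the change of AFS score cannot be assumed, the tertiles of the parameter will be used as a dependent parameter", with an ordinal logistic model. A general sentence in the same row, "Randomization being stratified on IUA severity, statistical analysis will be adjusted on IUA severity", presumably covers the fallback too, although the fallback sentence does not repeat it.

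The Sample Size Calculation row rests on means alone: "Control group: mean difference of AFS score = 5 Study group: mean difference of AFS score = 6" and "Standard deviation: 1,8", two-sided 5%, 90% power, giving 138 evaluable and 154 randomized. It contains no odds ratio, category probabilities or power for a three-category outcome.

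**The concern.** If the trigger fires, the primary hypothesis is tested by a method that the sample size was not built for. The tertile cut treats all changes within a third as equal, so the model loses the ordering inside each third. Rank and ordinal methods also avoid the normality assumption but keep that ordering. The plan would therefore give up power in the situation where it needs a robust method, without gaining anything that an uncut method does not offer.

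The trigger is also worded in terms of the change itself. The raw change pools two arms and two severity strata, so it need not be normal even when the ANCOVA model is correct. What is at stake is the chance of detecting a real benefit, not the risk of a false claim of superiority.

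**Working it through.** **1. The plan's own figure.** Inputs from the Sample Size Calculation row: difference 6 − 5 = 1, SD 1.8, "Two sided test" at 5%, power 90%.

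- n per arm = 2 × (1.960 + 1.282)² × 1.8² / 1² ≈ 68.1, rounded up to 69, so 138 in total.
- With 10% loss: 138 / 0.90 = 153.3, rounded up to 154.
- Power at 69 per arm: z = 1 / (1.8 × √(2/69)) = 3.263; 3.263 − 1.960 = 1.303; Φ(1.303) = 90.4% (90.0% by noncentral t).

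Both 138 and 154 reproduce. They apply to the comparison of means only.

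**2. Power of the fallback.** Two sets of simulations were run, with 3,000 and 4,000 trials per case. Each used 69 per arm, a location shift of 1, SD 1.8, two severity strata of about equal size and a stratum term in every model. Tertiles were cut on the pooled data, and rounded scores were run with ties assigned low and ties assigned high. Monte Carlo standard error is at most 0.5/√3000 = 0.9 points. Shapes, whole-number scoring, stratum split and stratum gaps are assumptions; the documents give none of them.

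No stratum effect, power in % (range over rounding, tie rule and simulation set):

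| Assumed shape | Tertiles, ordinal model | Uncut, van Elteren | ANCOVA |
|---|---|---|---|
| Normal, continuous | 82.0–82.2 | 88.2–88.6 | 90.1–90.4 |
| Normal, rounded | 79.6–82.5 | 87.2–88.8 | 89.1–90.6 |
| Uniform | 62.8–67.7 | 84.3–86.3 | 88.7–89.9 |
| Two-peaked | 78.7–84.5 | 88.8–92.2 | 89.1–89.9 |
| Moderate skew (gamma, shape 4) | 80.3–89.6 | 92.3–93.3 | 88.9–90.0 |
| Strong skew (exponential) | 81.2–97.4 | 98.4–99.4 | 87.7–89.9 |
| Heavy tails (t, 4 df) | 94.7–95.3 | 95.8–96.5 | 88.7–90.0 |
| Heavy tails (Laplace) | 95.8–96.8 | 95.5–97.1 | 88.9–90.5 |
| 20% recurrence mixture | 78.4–95.2 | 94.0–95.6 | 88.7–90.1 |

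In the 3,000-trial set, proportional-odds regression on the full rounded score was within 1 point of van Elteren (rounded normal 89.2%, uniform 84.9%, t 96.1%).

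**3. Is the ordering universal?** No. In the 4,000-trial set, tertiles were below van Elteren in 45 of 48 runs, by 0.5 to 40 points. The exceptions were rounded Laplace under both tie rules (96.8% and 96.6% against 95.7%) and the rounded recurrence mixture under one tie rule (94.7% against 94.0%). Fresh runs confirmed these as advantages of about 1.0–1.2 and 0.6 points.

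**4. Stratum effect.** The plan does not say whether 1.8 is the SD within stratum or within arm, and the answer matters.

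- *1.8 within stratum, 2-point gap added:* tertile power was 50–96% across shapes. Rounded normal gave 77.6–78.3% against 87.3% for van Elteren. Continuous two-peaked gave 50.5% against 91.0%. The heavy-tailed shapes were then up to about 6 points below van Elteren.
- *1.8 within arm, gap included:* with equal strata and a 2-point gap, the within-stratum SD is √(1.8² − 1²) = 1.50. Rounded normal gave about 89% for tertiles against 96–97% for van Elteren. With a 3-point gap, tertiles reached 99% and van Elteren 100%.
- *Change capped at an assumed baseline score (5–8 moderate, 9–12 severe), 1.8 within arm, gap 0, 1, 2, 3:* tertiles 78–82%, 83–86%, 90–92%, 99%; van Elteren 89%, 92%, 98%, 100%.

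**5. Trigger.** The plan names no test, so Shapiro-Wilk at 5% is an assumption. On normal data rounded to whole numbers it fired in 100% of trials when applied to the raw change and in 35% when applied to residuals. Power of the two-stage procedure was then 81–83% and 88% respectively. For a continuous normal score both versions fired in about 5%.

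**6. Type I error.** Under the null, rejection was 4.5–5.9% for the tertile model and 5.0–5.9% for the two-stage procedure.

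**The case against.** The tertile model is a contingency, and the absence of a power calculation for a contingency does not make it underpowered. About 20 of the 48 runs reached 90% or more. The very low figures come from uniform and two-peaked shapes, which nothing in the documents supports; without the uniform shape, the no-gap range is roughly 78–97%. Where a normality check would fire because of heavy tails, tertiles beat ANCOVA by about 5–7 points, and for strong skew they can do so depending on the tie rule. All of this stands, and it limits the size of the point.

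The document is headed "PREG2 protocol synopsis", so a fuller plan may specify the normality test, threshold and tie rule. Their absence here is missing detail and is not counted as a fault. The objection does not reach the tertile cut, which is stated here.

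A reader might infer that the tertile model always loses to an uncut test. The reversals in step 3 rule that out. A reader might also infer that ANCOVA must be primary whatever the data look like. The power results do not require that: ANCOVA was steady at 88–91% in the no-gap cases, but below tertiles for heavy tails and sometimes for strong skew.

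**Conclusion.** The point holds as a cheap improvement of lower severity. The fallback is stated, no power is given for it, and it usually has less power than a severity-adjusted analysis of the uncut change. The loss is about 5–9 points for a rounded normal score with no stratum effect and about 20 points for a uniform shape. For heavy tails with no stratum effect the difference is about 1–2 points either way. The overall range of about 50% to 99% describes the settings tried and is not a bound; it depends on shape, tie rule, stratum gap and the meaning of the 1.8. The documents support saying that power can fall well short of 90%, not that it will. They do not support a claim of inflated false positives.

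**What to change.** If a non-normality fallback is kept, replace the tertile sentence with wording such as:

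> If the residuals of the stratum-adjusted ANCOVA depart from normality by the pre-specified criterion, the full AFS change will be analysed without grouping, adjusted for severity stratum, by proportional-odds regression (or the van Elteren test).

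One of the two methods should be chosen in advance. The check should be applied to the model residuals and not to the raw change. The success criterion, now written in mean changes, needs a matching statement of direction for the chosen method.

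An acceptable alternative is to keep ANCOVA as primary regardless of the normality check and pre-specify the uncut analysis as a sensitivity analysis. That is a preference.

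The cost is wording in the synopsis and the SAP, with no extra patients or data. The fallback result would be an odds ratio or a rank test instead of a mean difference; the tertile model does not give a mean difference either.
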